#### **Introduction**

To date, no prospective trials have been conducted evaluating the outcomes of duration of antibiotic prophylaxis with bladder onabotulinumtoxinA injection. Antibiotic regimens vary widely from study to study, with differing indication (idiopathic vs neurogenic overactive bladder), pre-procedural urine studies (sterile urine culture, negative urinalysis, asymptomatic bacteriuria), route (intramuscular or oral), duration (zero to seven days), dose, and class of antibiotic (Aharony et al., 2020; Houman et al., 2019; Leitner et al., 2016; Bickhaus et al., 2020). In published studies, injection protocols have or have not included an antibiotic prophylactic treatment (Hermieu et al., 2014). Much of the original literature supporting onabotulinumtoxinA use for refractory overactive bladder does not provide specifics on antibiotic prophylaxis regimen (Aharony et al., 2020). The goal of this study is to determine if the incidence of post-procedure UTI is similar between single-dose and multi-day durations of peri-procedural antibiotics.

#### **Background and Significance**

Bladder onabotulinumtoxinA is a widely used third-line treatment option for patients with refractory overactive bladder, including symptoms associated with neurological disease. (Lightner et al., 2019). The most common adverse event related to bladder onabotulinumtoxinA injection is postoperative urinary tract infection (UTI). In some studies, rates of UTI are reported as high as 64% following bladder onabotulinumtoxinA (Yunfeng et al., 2022). Within our institution these rates are much lower at 11% (Martin et al., 2022).

Despite post-procedure UTI as a commonly reported adverse event, there are no specific guidelines for antibiotic prophylaxis for bladder onabotulinumtoxinA injection for prevention of UTI. The most recent American Urological Association (AUA) best practice statement for urologic procedures and antimicrobial prophylaxis does not provide specific recommendations for antibiotic prophylaxis for bladder onabotulinumtoxinA injection (Lightner et al., 2020). The recommendation for cystourethroscopy with minor manipulation with break in mucosal barriers, biopsy, fulguration, etc., is uncertain for the indication for antibiotic prophylaxis (Lightner et al., 2020). If prophylactic antibiotics are administered, a single dose of trimethoprim-sulfamethoxazole or amoxicillin/clavulanate is the recommended regimen, considering patient specific risk factors and prior urine culture results (Lightner et al., 2020). The product information guide from the manufacturer for bladder onabotulinumtoxinA recommends prophylactic antibiotics be administered 1–3 days pre-treatment, on the treatment day, and 1–3 days post-treatment to reduce the risk of procedure-related UTI (BoTox R, Allergan, Inc., Irvine, CA). Our own retrospective

study demonstrated no additional benefit from a multi-day course of antibiotic compared to single dose (Martin et al., 2022).

The current era of increasing healthcare-related costs, adverse events, and growing MDR (multidrug resistant organisms) calls for use of antimicrobials only when medically necessary and with the narrowest spectrum of activity with the shortest duration possible (Lightner et al., 2020). There is no high-level evidence to support the use of multiple doses of antimicrobials in the absence of preoperative symptomatic infection (Lightner et al., 2020). To date, no prospective trials have been conducted to evaluate the impact of duration of antibiotic prophylaxis on incidence of UTI after bladder onabotulinumtoxinA injection. The paucity of data has led to a lack of definitive guidance on best practice on an international level (Hermieu et al., 2014; Lightner et al., 2019). The goal of this study is to determine if duration of antibiotic prophylaxis is associated with the incidence of post-procedure UTI after office bladder onabotulinumtoxinA injection. Subjects will be randomized to receive one dose of pre-procedure antibiotic or one dose of pre-procedure antibiotic with continuation of the antibiotic for 3 days total. We hypothesize that a single dose of antibiotic prophylaxis is as effective as a multiple day course in the prevention of UTI with bladder onabotulinumtoxinA injection.

## **Study Design**

### **Design & Population:**

Men and women 18 years of age or older undergoing bladder onabotulinumtoxinA in the office will be randomized in a 1:1 ratio into one of two groups until the targeted sample size is met:

- The single dose group will receive one dose of oral antibiotic prior to bladder onabotulinumtoxinA injection.
- The multi-dose group will receive one dose of antibiotic prior to bladder onabotulinumtoxinA injection and additional antibiotics for a total of three days of antibiotic administration.

Random permuted block randomization with block sizes of 2, 4, 6, and 8 will be used to assign eligible patients to treatment groups, determined by a computer program.

Eligibility will be assessed based on the following inclusion/exclusion criteria:

### **Inclusion Criteria:**

- Participants with planned in-office bladder onabotulinumtoxinA injection
- Men or Women Age  $\geq 18$
- Able to read, speak, and write in English
- No contraindication to injection of onabotulinumtoxinA - hypersensitivity to any botulinum toxin preparation or to any of the components in the formulation
- Willingness and ability to initiate intermittent catheterization post-treatment if required
- No contraindication to oral antibiotics
- No active antibiotic therapy for any indication at the time of onabotulinumtoxinA injection

- Have not participated in this study before

#### **Exclusion Criteria:**

1. Any type of catheterization to empty the bladder
2. Unwillingness or inability to initiate intermittent catheterization post-treatment if required
3. Less than 3 months since last bladder onabotulinumtoxinA injection
4. Pregnant and/or breastfeeding
5. Active symptomatic UTI the day of the procedure - new or worsening frequency, urgency, dysuria, hematuria, suprapubic/flank pain, fevers or chills
6. History of recurrent UTI
7. Prior development of urinary retention or incomplete bladder emptying after bladder onabotulinumtoxinA injection requiring catheterization of any type

#### **Sample Size:**

Sample Size: 100

In its recommendations for development of new drugs for treatment of complicated UTI, the FDA suggests using a noninferiority margin of no more than 10%; however, this margin may be relaxed.

It is assumed that approximately 10% of patients will experience a UTI, based on our previous single institution study among a similar cohort of patients. Based on a one-sided 95% confidence interval (or equivalently 90% two-sided confidence interval) and no loss to follow-up, with 90% statistical power and 20 % inferiority margin the total sample size is 96 with 48 allocated to each group. \*\*Want to add 20% to this number to account for drop out or loss to follow up.

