**Aims:**

Primary Aim:

- Establish noninferiority of the single dose antibiotic administration to the multi-dose antibiotic administration.

To assess this aim, the rate of postoperative urinary tract infection (UTI) within 4 weeks following bladder onabotulinumtoxinA injection will be compared between groups. Noninferiority will be declared if the incidence of UTI in the single dose group is not more than UTI incidence in the multiple dose group within statistical variability, by the prespecified noninferiority margin.

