#### Data Analysis

The analysis will be conducted using intention-to-treat (ITT) principles. Baseline characteristics of subjects in each group will be summarized using median (IQR) for continuous variables and frequency (percentage) for categorical variables. A 95% confidence interval for the difference between UTI rates (single dose minus multi-dose) will be calculated; noninferiority will be established if the upper limit of the 95% confidence interval exceeds the noninferiority margin.

An adjusted odds ratio will be estimated via logistic regression to determine and quantify the association between the treatment group and odds of experiencing urinary retention.

Incidence of adverse events will be summarized and compared using chi-square or Fisher's exact test, as appropriate.

All analyses will be performed using R statistical software by the Glickman Urological and Kidney Institute biostatistics team.

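### The 20-point noninferiority margin is twice the assumed UTI rate, has no reason attached to it, and the plan does not limit what meeting it may be said to show

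*Combined protocol and SAP*

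**What the plan says.** All references are to the combined protocol and SAP.

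- **Sample Size.** The event rate is given as "It is assumed that approximately 10% of patients will experience a UTI". One benchmark is cited, for "drugs for treatment of complicated UTI, the FDA suggests using a noninferiority margin of no more than 10%; however, this margin may be relaxed". The calculation follows: "Based on a one-sided 95% confidence interval (or equivalently 90% two-sided confidence interval", no losses, and "with 90% statistical power and 20 % inferiority margin the total sample size is 96", or 48 per group. This is the only place where the 20 appears.
- **Aims.** The primary aim is noninferiority of single dose to multi-dose, judged "within statistical variability, by the prespecified noninferiority margin". No number is given.
- **Data Analysis.** A 95% confidence interval for single dose minus multi-dose is planned, without saying whether it is one- or two-sided. The rule reads: "noninferiority will be established if the upper limit of the 95% confidence interval exceeds the noninferiority margin". Again no number is given.
- **Introduction.** The goal is to "determine if the incidence of post-procedure UTI is similar between single-dose and multi-day durations of peri-procedural antibiotics".
- **Background and Significance.** The hypothesis is that "a single dose of antibiotic prophylaxis is as effective as a multiple day course in the prevention of UTI". This section also gives general grounds for accepting some loss. There is no high-level evidence for repeated doses, the indication for prophylaxis is uncertain, a single dose is the recommended regimen if any is given, the site's own retrospective study found no added benefit from a multi-day course, and there is antibiotic stewardship.

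**The concern.** The margin is twice the event rate it is meant to protect and twice the only benchmark cited. That benchmark concerns treatment of complicated UTI, so it applies to prophylaxis only loosely. Saying that a margin may be relaxed does not say why 20 points is the right place to stop, and the general grounds in the background do not lead to that number either.

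The second gap is in the conclusion. The formal aim is correctly noninferiority, but the stated goal and hypothesis use stronger language, and no section says how a positive result is to be worded. A result that excludes only a 20-point increase could be published as showing that single dose performs as well as three days. Readers deciding on antibiotic duration would then be told more than the trial had shown.

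**Working it through.** **Inputs.** UTI rate 10% in both arms, margin 20%, power 90%, 1:1 allocation, 48 per group (Sample Size). Planned total 100 (Sample Size). Assumption: 40 per group stands for 20% loss from 50. Success is read throughout as upper limit *below* the margin.

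**1. Reproduce 48 per group.** n = 2p(1-p)(z + 1.2816)² / margin², with p = 0.10:

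- Two-sided 95% (z = 1.96): 0.18 × (3.2416)² / 0.04 = 47.3, so 48 per group, total 96.
- One-sided 95% (z = 1.645): 0.18 × (2.9266)² / 0.04 = 38.5, so 39 per group, total 78.
- One-sided 95% with continuity correction, (n/4)[1 + √(1 + 4/(n × 0.20))]² at n = 38.5: about 48.02 per group.

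The stated 48 therefore fits two-sided 95% without correction, or one-sided 95% with it (48.02 taken as 48). It does not settle which was meant. It does settle the scale: a relative 20% (2 points) would need 0.18 × (2.9266)² / 0.0004, about 3,850 per group.

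**2. What meeting the margin excludes.** 20/10 = 2.0 times the assumed rate (20/11 = 1.8 times the 11% institutional rate given in the background). With multi-dose at 10%, it excludes a single-dose rate of 10 + 20 = 30% or more.

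**3. Chance of passing.** Exact enumeration of two independent binomials, multi-dose rate 10%. Each cell gives Wald / Newcombe / Miettinen-Nurminen score, in %.

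| Single-dose rate | Margin | n per group | Two-sided 95% | One-sided 95% |
|---|---|---|---|---|
| 10% | 20 | 48 | 90.1 / 87.0 / 85.1 | 93.7 / 93.2 / 92.1 |
| 10% | 20 | 40 | 85.7 / 79.5 / 79.3 | 90.2 / 88.8 / 86.6 |
| 20% | 20 | 48 | 31.2 / 28.1 / 25.5 | 40.0 / 40.0 / 37.4 |
| 20% | 20 | 40 | 27.6 / 23.4 / 22.5 | 36.1 / 35.5 / 32.2 |
| 30% (boundary) | 20 | 48 | 3.1 / 2.8 / 2.4 | 5.3 / 5.5 / 5.0 |
| 10% | 10 | 48 | 41.5 / 33.7 / 33.7 | 50.9 / 45.9 / 45.6 |
| 10% | 10 | 40 | 37.8 / 26.1 / 26.0 | 47.5 / 42.4 / 42.4 |
| 20% | 10 | 48 | 3.3 / 2.5 / 2.5 | 5.5 / 5.1 / 5.0 |

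**4. Observed results.** For 10/48 versus 5/48 the difference is 0.104 and its standard error is √(0.2083 × 0.7917/48 + 0.1042 × 0.8958/48) = 0.0733. The Wald upper limit is 0.104 + 1.96 × 0.0733 = 0.248, or 0.225 with 1.645. Newcombe gives 0.251 and 0.227; the score method gives 0.256 and 0.230. An observed doubling fails at either level. With 5/48 on multi-dose, the most single-dose events that pass are 8 (Wald) or 7 (Newcombe, score) at two-sided 95%, and 8 by all three at one-sided 95%.

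**5. A 10-point primary margin instead.** The formula in step 1 with margin 0.10 gives 189.1 (two-sided 95%) or 154.1 (one-sided 95%), that is 190 or 155 per group.

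**The case against.** The best defence is that a wide margin is reasonable here. The benchmark is for treatment, evidence for multi-day prophylaxis is weak, stewardship argues for the shorter course, and a 10-point margin would need three to four times as many patients. The wording about similarity and effectiveness is a goal and a hypothesis, not a reporting rule. The formal aim is noninferiority, and the planned interval lets any reader compare its limit with 10 or 20 points.

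Much of this stands. The grounds support accepting some loss, but none leads to 20 points. The documents give no UTI rate without prophylaxis for this population, so the share of benefit given up at 20 points cannot be worked out. The planned interval helps a careful reader but does not constrain the stated conclusion.

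Four stronger readings are tempting and are not supported:

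- *The false-positive rate is inflated.* It is not. A true 20% versus 10% is inside the margin, so passing is the rule working as set. At the boundary, 30% versus 10%, the pass rate is near nominal. Nothing in the documents suggests that a doubling is likely.
- *An observed doubling would be called noninferior.* It fails at both levels.
- *The margin breaches a binding 10% limit.* The cited figure is a suggestion for another setting, and the plan says it may be relaxed.
- *The plan's 48 per group proves a two-sided 95% limit was intended.* One-sided 95% with continuity correction gives essentially the same number, and the only level stated with its sidedness is one-sided 95%.

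**Conclusion.** The point holds as a limit on interpretation and a gap in justification, not as an error in the sample size. The 20-point margin is twice the assumed rate, no reason is attached to that number, and a positive result would not by itself support a claim of similar incidence or equal effectiveness. A true doubling would meet the margin in roughly one trial in four to two in five at 48 per group, depending on confidence level and interval method.

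These figures assume a 10% multi-dose rate, independent binomial outcomes, an absolute margin (inferred from the sample size), and success as upper limit below the margin. The last is needed because the rule under Data Analysis, as written, declares noninferiority when the limit is above the margin. That reversal is wrong whatever margin is chosen. It is corrected in the same edit and adds no weight to the argument about the margin.

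**What to change.** Keep the sample size and the 20-point primary test.

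1. Under Data Analysis, require the upper limit to be below 20 percentage points, absolute. State that number under Sample Size, Aims and Data Analysis, with the reason an increase just short of it is acceptable for prophylaxis. If no reason can be given, say so; step 3 then matters all the more.
2. Use one confidence level under Sample Size and Data Analysis, name the interval method, and restate power for that choice. With Newcombe, power is about 87% (two-sided 95%) or 93% (one-sided 95%) at 48 per group, and about 80% or 89% at 40.
3. Pre-specify that meeting the margin is reported as excluding an absolute increase in UTI of 20 points or more, and not as similarity or equal effectiveness.
4. If the margin is met, compare the same upper limit with 10 points in fixed sequence, reported as excluding an increase of 10 points or more. This costs no alpha. State that power is low: with Newcombe at 48 per group, about 34% (two-sided 95%) or 46% (one-sided 95%).

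Cost: text changes only, with no extra patients or data. The downsides are a narrower claim if only 20 points is met, and an open admission of low power at 10 points. Making 10 points the primary margin is not proposed, given the 155 to 190 per group it would need.

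### The sample size rests on a two-sided 90% interval, but the decision rule uses an unqualified 95% interval with no method named

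*Combined protocol and SAP*

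**What the plan says.** The Sample Size section states the error rate behind the design: "Based on a one-sided 95% confidence interval (or equivalently 90% two-sided confidence interval"). Its other inputs are a 10% UTI rate ("It is assumed that approximately 10% of patients will experience a UTI"), no loss to follow-up, and the result "with 90% statistical power and 20 % inferiority margin the total sample size is 96 with 48 allocated to each group". It names no formula.

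The Data Analysis section gives the operative rule: "A 95% confidence interval for the difference between UTI rates (single dose minus multi-dose) will be calculated", followed by "noninferiority will be established if the upper limit of the 95% confidence interval exceeds the noninferiority margin". It does not say whether the interval is one- or two-sided, does not say how it is computed, and does not refer back to the sample size section.

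The Primary Aim asks that the single-dose rate be no higher than the multi-dose rate "within statistical variability, by the prespecified noninferiority margin". It gives no level, sidedness or method.

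**The concern.** An interval with an upper limit, described only as 95%, is ordinarily two-sided. Comparing its upper limit with the margin is then a one-sided test at 2.5%, half the 5% on which the trial was sized. The Sample Size section itself separates one-sided 95% from two-sided 90%, so the missing qualifier in Data Analysis matters.

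This is the decision rule for the only primary aim. Two analysts who each follow the document faithfully, one from each section, could reach opposite conclusions on the same data. With the method also open, the choice could be made after the results are seen.

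**Working it through.** **Inputs.** From Sample Size: UTI rate 10%, margin 20 percentage points, power 90%, no loss, 48 per group. From Design & Population: 1:1 allocation. Assumed, because the plan does not say so: a true difference of zero (10% in both arms).

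**Reproducing the 96.** Unpooled normal formula, with z = 1.282 for 90% power:

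n per group = (z_alpha + z_power)² × 2 × 0.1 × 0.9 / 0.2²

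- One-sided 5% (z = 1.645): 38.54, so 39 per group, 78 in total.
- One-sided 2.5% (z = 1.960): 47.28, so 48 per group, 96 in total.

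Continuity correction, n/4 × (1 + √(1 + 4/(0.2n)))²: 48.02 per group at one-sided 5%, and 56.84 at 2.5%.

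The plain formula returns 96 only at the alpha the section does not state. A corrected formula at the stated alpha comes to 48.02. With no method named, 96 is not shown to be wrong, and it does not prove which interval was meant.

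**Power at 48 per group, unpooled formula.** Φ(0.2/√(0.18/48) − z_alpha) = 94.75% at one-sided 5% and 90.42% at 2.5%.

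**Exact operating characteristics.** These sum the two-binomial probabilities over all 49 × 49 outcomes. Noninferiority is declared when the upper limit is below 20 points. Each pair is 90% interval / 95% interval (both two-sided).

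| Method, 48 per group | Power, 10% vs 10% | Difference (points) | False noninferiority, 30% single-dose vs 10% multi-dose |
|---|---|---|---|
| Wald | 93.7% / 90.1% | 3.6 | 5.3% / 3.1% |
| Newcombe | 93.2% / 87.0% | 6.2 | 5.5% / 2.8% |
| Score | 92.1% / 85.1% | 7.0 | 5.0% / 2.4% |
| Wald with continuity correction | 90.1% / 84.6% | 5.5 | 3.3% / 1.5% |

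Any result that passes with the 95% interval also passes with the 90% interval. The power difference is therefore the share of trials, under the design assumptions, in which the verdict depends on the section followed.

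At the headline size of 100 (50 per group, no loss), the power pairs in the same order are 94.8/91.7, 93.7/87.9, 93.7/86.7 and 91.2/84.3%.

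**Example: 7/48 single-dose against 3/48 multi-dose.** The difference is 4/48 = 0.0833, with unpooled standard error 0.0618.

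- Wald: 0.0833 + 1.645 × 0.0618 = 18.5%; 0.0833 + 1.960 × 0.0618 = 20.4%.
- Newcombe: 19.2% and 21.6%.
- Score: 19.5% and 21.9%.
- Continuity-corrected Wald adds 1/48 = 0.0208: 20.6% and 22.5%. It fails both ways here, but reverses on 8/48 against 5/48 (19.8% and 22.0%).

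With 4/48 UTIs in the multi-dose arm, the largest single-dose count that passes falls by one under every method: from 8 to 7 (Wald, Newcombe) or from 7 to 6 (score, continuity-corrected Wald).

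**Method matters by itself.** For 8/48 against 5/48 the two-sided 95% limit is 19.9% by Wald and 20.4% by Newcombe, on opposite sides of the margin.

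**The case against.** The strongest reply is that there is no contradiction. Sample Size defines its level as one-sided 95%, Data Analysis says 95% and uses only the upper limit, so both may mean the same bound. That reading is possible, and it makes the defect an ambiguity that becomes a conflict only under the usual two-sided reading. But nothing in the text selects it.

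A second reply is that the 96 reveals the intent. The unpooled formula at 2.5% gives exactly 48 per group, while the continuity-corrected 48.02 strictly rounds up to 49 (98 in total). On that view the sample size sentence misdescribes its own alpha, and the size already suits a two-sided 95% Wald interval. This is plausible, but it is an inference about an unnamed method, and it would itself mean that the stated alpha needs correcting.

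Third, neither reading is reckless. The two-sided 95% rule is stricter than the declared alpha, and the 90% rule has a false-noninferiority risk of at most 5.5% in the cases above, close to the declared 5%. With Wald at two-sided 95%, the stated 90% power holds (90.1% exact). All of this stands. It shows that either choice can be defended once made, not that the choice can stay open.

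Finally, the missing method and the reversed direction of the rule are separate defects. That is fair. They are raised here because they sit in the same sentences, and the sizes given above do not draw on the reversal.

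**Conclusion.** The concern holds and should be resolved before any outcome analysis. As ordinarily read, the alpha behind the stated size and power is not the alpha of the rule that decides the trial, and no section fixes the level, sidedness or method. For a given method, the 90% interval carries 1.7 to 2.1 times the false-noninferiority risk of the 95% interval, and the 95% interval costs about 4 to 7 points of power. The stated total of 96 is not shown to be wrong.

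These sizes assume 48 per group with no loss, 10% in both arms for power, 30% against 10% for the error rate, and noninferiority declared when the upper limit is below 20 points. That last assumption reverses the direction printed in Data Analysis.

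**What to change.** State the same one-sided alpha, confidence level with sidedness, and named interval method in Sample Size and Data Analysis. The choice is the sponsor's.

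- **Keep one-sided 5%.** Data Analysis should specify a one-sided 95% (two-sided 90%) interval. Sample Size should name the method that gives 96 or restate the power (about 95% at 48 per group by the unpooled formula). No extra patients are needed. The price is a false-noninferiority risk near 5% with Wald, Newcombe or score.
- **Adopt two-sided 95%.** Sample Size should state a one-sided alpha of 2.5%. With unpooled Wald and no loss, 96 gives about 90% power and no extra patients are needed. With other methods, restate the power (exact 87.0% Newcombe, 85.1% score). To reach about 90% with a score interval, exact power is 89.9% at 54 and 91.0% at 55 per group; 55 per group is 110 in total, 14 more than 96.

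In the same edit, change the Data Analysis rule so that noninferiority is declared when the upper limit is below the margin. If 96 and unpooled Wald are kept, the whole cost is wording.

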#### **Research Procedures**

##### **Protocol:**

- After informed consent is obtained, urinalysis will be collected. Post-void residual will also be assessed by bladder scan if not already documented in the electronic medical record in the prior three months.
- Patients with positive urinalysis and symptomatic for UTI will be excluded from the study.
- Patients will be randomized in a 1:1 ratio to one of two groups.
  - Group 1 will receive one dose of antibiotic prior to bladder onabotulinumtoxinA injection.
  - Group 2 will receive one dose of antibiotic prior to bladder onabotulinumtoxinA injection. The same antibiotic will be continued for 3 days of total antibiotic administration with additional doses prescribed to the patient's pharmacy.
- Bladder onabotulinumtoxinA injection and dosing will be completed based on the surgeon's standard technique and template.
- Bladder onabotulinumtoxinA injection will be completed by staff or fellows in the Female Pelvic Medicine and Reconstructive Surgery division of the Genitourinary and Kidney Institute.
- Patients will be followed for 4 weeks after the procedure.

- At 4 weeks study investigators will contact the patient by phone to evaluate for any UTIs or adverse events not previously reported by the patient during the study period.
- Chart review will occur in 4 weeks to assess any unreported events.
- Other than this additional phone call, post-operative patient management will not deviate from the standard of care.
- Patients will be instructed to report symptomatic UTIs, urinary retention, or any other adverse events related to onabotulinumtoxinA or antibiotic to investigators.
- Patients that report symptoms suggestive of a UTI will result in obtaining a urine culture.
- Symptomatic, culture proven UTIs will be treated with appropriate antibiotics per the current AUA guidelines.
- Symptoms suggestive of urinary retention, such as increased urinary frequency, voiding small amounts of urine, or feelings of incomplete bladder emptying, will result in obtaining a post void residual (PVR) and urinalysis.
- Patients will undergo teaching to perform self, clean intermittent catheterization of the bladder per the discretion of the operating surgeon.
- Any adverse reactions to the prescribed antibiotic will result in discontinuation of the antibiotic and managed according to the severity of the reaction.

Antibiotic regimens:

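### The target of 100 does not contain the 20% loss allowance requested on the derived 96; it leaves room for 4%, and the power cost depends on an interval method the plan does not name

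*Combined protocol and SAP*

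**What the plan says.** All in the combined protocol and SAP:

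- The Sample Size section opens with "Sample Size: 100". The Study Design section randomizes patients until the target is reached, so 100 counts patients randomized, not patients with a known outcome.
- The basis of the calculation is "Based on a one-sided 95% confidence interval (or equivalently 90% two-sided confidence interval) and no loss to follow-up". The result is "with 90% statistical power and 20 % inferiority margin the total sample size is 96 with 48 allocated to each group". The assumed UTI rate is about 10%.
- The same paragraph ends with a starred sentence: "Want to add 20% to this number to account for drop out or loss to follow up". No inflated total follows there or in any other section.
- The Data Analysis section says "A 95% confidence interval for the difference between UTI rates (single dose minus multi-dose) will be calculated", without stating whether the interval is one- or two-sided or how it is computed. It also says "The analysis will be conducted using intention-to-treat (ITT) principles".
- On follow-up, the Research Procedures section says "Patients will be followed for 4 weeks after the procedure" and "At 4 weeks study investigators will contact the patient by phone to evaluate for any UTIs or adverse events". A chart review at 4 weeks is added to pick up unreported events.

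**The concern.** One section holds three statements that cannot all be true: a target of 100, a no-loss requirement of 96, and a wish to enlarge that requirement by a fifth. The gap between 96 and 100 is 4 patients. A reader cannot tell whether the 20% was dropped, forgotten, or believed to be inside the 100, and so cannot tell what power is left if outcomes go missing. In a noninferiority trial, lost power means a greater chance of failing to show noninferiority when the single dose really is no worse.

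**Working it through.** **Inputs.** From Sample Size: UTI rate 10% (taken here as equal in both arms), margin 20 percentage points, power 90%, one-sided 95% confidence, no loss, 96 total, target 100, 20% to be added. From Study Design: 1:1 allocation. From Data Analysis: a 95% interval, sidedness not stated.

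**Reproducing the 96.** The plain normal formula is n per arm = (z_alpha + z_0.90)^2 x 2 x 0.1 x 0.9 / 0.2^2.

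- One-sided 0.05, the level stated in Sample Size: (1.645 + 1.282)^2 x 0.18/0.04 = 38.54, so 39 per arm, 78 total. This is not 96.
- One-sided 0.025, the level of a two-sided 95% interval: (1.960 + 1.282)^2 x 0.18/0.04 = 47.28, so 48 per arm, 96 total. This matches.
- One-sided 0.05 with continuity correction, n/4 x (1 + sqrt(1 + 4/(n x 0.2)))^2 at n = 38.54: 48.02 per arm. This is 96 to the nearest whole number, or 98 under the usual rounding up.

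Two routes therefore lead to 96, and the plan does not say which was used.

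**Applying the allowance.**

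- 96 x 1.20 = 115.2, so 116 (58 per group).
- 96/0.80 = 120 (60 per group).
- Loss tolerated by 100 relative to 96: 1 - 96/100 = 4%.
- 100 less 20% = 80, or 40 per arm, 16 short of 96.

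**Power.** Uncorrected: Phi(0.2/sqrt(0.18/n) - z_alpha). Continuity-corrected: Phi((0.2 - 1/n)/sqrt(0.18/n) - z_alpha).

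| Interval | 48 per arm | 45 per arm (10% loss) | 40 per arm (20% loss) |
|---|---|---|---|
| Uncorrected, two-sided 95% | 90.4% | 88.5% | 84.6% |
| Continuity-corrected Wald, one-sided 95% | 90.0% | 87.8% | 83.2% (exact 83.0%) |
| Uncorrected Wald, one-sided 95% | 94.8% | not computed | 90.9% (exact 90.2%) |

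Exact figures enumerate both binomials. At 40 per arm and one-sided 95%, other common intervals fall in between: Newcombe 88.8% and score 86.7%, both exact.

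**Loss at which 90% is reached, from 100 enrolled.**

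- Uncorrected two-sided 95%: 95 evaluable (47 and 48) gives 90.1% and 94 gives 89.8%, so about 5% loss.
- Continuity-corrected at one-sided 95%: 48 per arm gives 90.0% by formula and 90.1% exact; 47 per arm gives 89.5% exact. So 4% loss.

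**Why 78 is conditional on the method.** Exact power at 39 per arm, one-sided 95%: uncorrected Wald 90.7%, Newcombe 87.2%, score 87.2%, continuity-corrected Wald 81.6%. Only the first reaches 90%.

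**The case against.** The strongest objection is that 100 may already be enough. At the one-sided 95% level that the Sample Size section states, the plain formula needs 78. Then 78/0.80 = 97.5, so 98, and 100 covers a 20% loss with 90.9% power. A reader might infer from the missing allowance that the trial is underpowered, or that 20% loss must take it below 90%. The documents do not support that stronger reading, because they name no interval method and one permissible method shows no shortfall. Nor do they support the opposite reading that the 20% is already built in: the plan gives its requirement as 96, asks for 20% on that number, and never derives 78. If 78 was intended, the 96 has to be restated, so the section needs correction either way.

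A second objection is that few outcomes will be lost. Follow-up lasts 4 weeks, a phone call and chart review may recover events, and under ITT a patient who stops the antibiotic is still counted. This stands as a limit on practical importance, and the documents forecast no loss rate. It does not remove the contradiction: ITT does not supply an outcome that was never obtained, and the Data Analysis section has no rule for missing outcomes.

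A third is that the starred sentence looks like a leftover drafting comment. It may be, but it sits in the section that fixes enrolment, and nothing shows whether it was acted on or abandoned.

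**Conclusion.** The point holds as an internal contradiction: 100 is neither 116 nor 120, and it tolerates 4% loss relative to 96. The consequence for power is moderate and conditional. On the two routes that return 96, a 20% loss lowers power from about 90% to about 83 to 85%, so the chance of missing true noninferiority rises from about 10% to about 15 to 17%. For an uncorrected Wald interval at one-sided 95% there is no fall below 90%. All of this assumes 10% UTI in both arms, a 20-point margin, equal or near-equal loss by arm, and no outcome recovered for lost patients. It should be corrected before the analysis, but the documents do not show that the trial will in fact lose 20% of its outcomes.

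**What to change.** Replace the starred note in Sample Size with one reconciled target.

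- **Without enrolling more:** keep 100, and state that it allows 4% loss relative to 96 and does not include the 20% allowance. Name the interval method and confidence level behind the requirement, consistently with Data Analysis, and give the power at 20% loss for that method: about 85% for an uncorrected two-sided 95% interval, or about 83% for a continuity-corrected Wald interval at one-sided 95%.
- **If an uncorrected Wald interval at one-sided 95% is chosen:** restate the requirement as 78 (98 after 20% loss) and the power at 20% loss as about 90 to 91%; the loss statement then refers to 78 instead of 96. For any other method, recalculate both figures.
- **If the 20% on 96 was intended:** the target should read 116 or 120, with the inflation formula stated. That means 16 or 20 more patients.

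The first two options cost wording only, with no extra patients, visits or data. The downside is that the quoted power may be less favourable.
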